6.3. End of Treatment Visit Assessment

The EOT Visit is a safety follow-up visit that is to be performed within 7 days (+/- 3 days) after the last dose of cabozantinib. All efforts should be made to conduct this visit. If it is not possible to conduct the EOT Visit, documentation of efforts to complete the visit should be provided.

The following procedures will be completed at the EOT Visit as designated in the Schedule of Assessments in Table 2.

- Physical examination
- Concomitant medication and procedures evaluation
- Vital signs (weight, temperature, sys/dias blood pressure, respiration rate, and pulse)
- ECOG performance status
- CBC, differential
- Clinical chemistry panel including fasting lipid panel and thyroid function tests
- Serum pregnancy test (women of child-bearing potential only)
- ECG
- Urinalysis with microscopic evaluation
- Adverse Event assessment
- Archival tumor collection (optional, for subjects undergoing clinical surgical resection)

6.4. Follow-up Period for Survival and Initiation of Anticancer Therapy

Adverse events will be monitored through 30 days after the subject's last dose of investigational product.

6.4.1. 30 Day Follow-Up Visit Therapy

The 30 day follow up visit should be completed 30 days after the subject's last dose of cabozantinib therapy (+/- 1 week).

The following procedures will be completed at the 30 day follow-up visit, as designated in the Schedule of Assessments in Table 2.

- Physical examination
- Concomitant medication and procedures evaluation
- Vital signs (weight, temperature, sys/dias blood pressure, respiration rate, and pulse)
- ECOG performance status
- Clinical chemistry panel including fasting lipid panel and thyroid function tests
- ECG
- Adverse Event assessment

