9.1.2. Serious Adverse Events (SAEs)

The SAE definition and reporting requirements are in accordance with the International Conference of Harmonisation (ICH) Guideline for Clinical Safety Data Management: Definitions and Standards for Expedited Reporting, Topic E2A.

An SAE is defined as any untoward medical occurrence that at any dose:

- Result in death;
- Is life-threatening (i.e., in the opinion of the investigator, the AE places the subject at risk of death; it does not include an event that, had it occurred in a more severe form, might have caused death);
- Requires subject hospitalization or results in prolongation of an existing hospitalization;
 - Note: While most hospitalizations necessitate reporting of an SAE, some hospitalizations do not require SAE reporting, as follows: elective or previously scheduled surgeries or procedures for pre-existing conditions that have not worsened after initiation of treatment (e.g., a previously scheduled ventral

hernia repair); pre-specified study hospitalizations for observation; or events that result in hospital stays of fewer than 24 hours and that do not require admission (e.g., an ER visit for hematuria that results in a diagnosis of cystitis and discharge home on oral antibiotics). SAEs must, however, be reported for any surgical complication resulting in prolongation of the hospitalization.

- Results in persistent or significant disability or incapacity:
 - Note: The term “disability” refers to events that result in a substantial disruption of a subject’s ability to conduct normal life function.
- Is a congenital anomaly or birth defect;
- Is an important medical event (IME):
 - Note: The term “important medical event” refers to an event that, based upon appropriate medical judgment, may not be immediately life-threatening or result in death or hospitalization, but may jeopardize the subject or require intervention to prevent one of the other serious outcomes listed. Examples of IMEs include intensive treatment in an emergency room or at home for allergic bronchospasm; blood dyscrasias, or convulsions that do not result in hospitalization; or development of product dependency or product abuse.

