9.1.3. Relationships to Study Treatment

Assessment of the relationship of the AE to the study treatment by the investigator is based on the following two definitions:

- Not Related: A not-related AE is defined as an AE that is not associated with the study treatment and is attributable to another cause or there is no evidence to support a causal relationship. Unrelated and unlikely related AEs should be documented as not related.
- Related: A related AE is defined as an AE where a causal relationship between the event and the study treatment is a reasonable possibility. A reasonable causal relationship is meant to convey that there are facts (e.g., evidence such as dechallenge/rechallenge) or other clinical arguments to suggest a causal relationship between the AE and study treatment. Possibly and probably related AEs should be documented as related.

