9.1.4. Serious Adverse Event Reporting

As soon as an investigator becomes aware of an AE that meets the definition of ‘serious,’ this must be documented on an SAE Report Form or in an electronic database and include the following:

- (i) all SAEs that occur after starting cabozantinib and through 30 days after the decision to discontinue study treatment and

- (ii) any SAEs assessed as related to study treatment or study procedures, from the time of informed consent, even if the SAE occurs more than 30 days after the decision to discontinue study treatment.

All SAEs that are assessed by the Sponsor-Investigator as related to drug or study procedure and all pregnancy/lactation reports regardless of outcome must be sent to Exelixis within one (1) business day of the Sponsor-Investigator's knowledge of the event. The reports must be sent to [contact] or [contact].

- The Sponsor-Investigator will perform adequate due diligence regarding obtaining follow-up information on incomplete reports. All follow-up information must be sent to Exelixis within one (1) business day of the Sponsor-Investigator's receipt of the new information. Upon Exelixis request, the Sponsor-Investigator will query for follow-up information.

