9.2.3. Follow-Up of Adverse Events

Any related SAEs or any AEs assessed as related that led to treatment discontinuation, including clinically significant abnormal laboratory values that meet these criteria, ongoing 30 days after the decision to discontinue study treatment must be followed until either resolution of the event or determination by the investigator that the event has become stable or irreversible. This follow-up guidance also applies to related SAEs still ongoing 30 days after the decision to discontinue study treatment. This does not apply to subjects who screen-fail. The status of all other continuing AEs will be documented as of 30 days after the decision to discontinue study treatment.

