11. CONCOMITANT MEDICATIONS AND PROCEDURES

All concomitant treatments, including blood and blood products, must be reported on the eCRF. Throughout the study, investigators may prescribe any concomitant medications or treatments deemed necessary to provide adequate supportive care except for those listed in Section 11.2.

Concomitant therapies are to be collected from enrollment/randomization through the EOT Visit. Therapy name including indication, dose, frequency, route, start date and stop date will be recorded on each subject's CRF(s).

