17.3. Case Report Forms

For enrolled subjects, all and only data from the procedures and assessments specified in this protocol and required by the eCRFs should be entered on the appropriate eCRF. Data from some procedures required by the protocol, such as physical examinations and laboratory results, will be recorded only on the source documents and will not be transcribed to eCRFs. Additional procedures and assessments may be performed as part of the investigator's institution or medical practice standard of care and may not be required for eCRF entry.

For each subject enrolled, the eCRF must be completed and signed by the PI or authorized delegate from the study staff.

The investigator should ensure the accuracy, completeness, legibility, and timeliness of the data in the eCRFs and in all required reports.

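### Counted from the last dose, routine adverse-event recording ends about when scheduled surgery can first occur, so non-serious post-operative wound complications are not systematically recorded

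*Combined protocol and SAP*

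**What the plan says.** **End of routine AE recording.** Section 6.4: "Adverse events will be monitored through 30 days after the subject's last dose of investigational product". Sections 10.1 and 12.1 also count 30 days from the last dose. Table 2 runs AE assessment to the 30-day follow-up visit, which has a tolerance of 7 days either way. Sections 9.1.1, 9.1.4 and 9.2.3 count from the decision to discontinue.

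**Earliest surgery.** Table 2 (footnote i), Section 6.2.1 and Table 8 require at least 28 days between the end of cabozantinib and scheduled surgery. Section 6.2.1 puts surgery typically 4 to 6 weeks after radiotherapy. Table 8 leaves resumption after surgery to clinical judgment, and Section 7.1.2 allows interruptions for surgical procedures.

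**What continues afterwards.**
- Section 9.1.4 keeps SAEs judged related to study treatment or study procedures reportable, "even if the SAE occurs more than 30 days after the decision to discontinue study treatment". Section 9.1.3 reads relatedness broadly: "Possibly and probably related AEs should be documented as related".
- Section 9.1.2: "SAEs must, however, be reported for any surgical complication resulting in prolongation of the hospitalization".
- Section 9.2.3 follows related SAEs and related AEs that led to discontinuation. Otherwise, "The status of all other continuing AEs will be documented as of 30 days after the decision to discontinue study treatment". Section 12.1 instead follows all SAEs, whatever their relationship, to resolution or sequelae.
- Section 6.4.2 lists a physical exam and imaging every 12 weeks to one year, ending earlier at recurrence. It lists no AE assessment.
- Section 17.3 says "all and only data from the procedures and assessments specified in this protocol and required by the eCRFs should be entered" on the eCRF. Data from some procedures, "such as physical examinations and laboratory results, will be recorded only on the source documents and will not be transcribed to eCRFs".
- Section 11: "Concomitant therapies are to be collected from enrollment/randomization through the EOT Visit". Section 11.1 and the visit list in Section 6.4.1 extend this to the 30-day visit.

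**The risk.** Section 1.1.3 links pre-operative radiotherapy to more wound-healing complications. Section 10.2.1 lists them among the medically important events with cabozantinib, and Table 8 warns that dehiscence can come long after a wound seems healed.

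**The concern.** Treatment here is given before an operation, and both of its components are described as impairing wound healing. The time in which that harm would show is the post-operative period, yet a window counted from the last dose closes at about its start. None of the remaining machinery picks up new non-serious events: the DLT period has closed by scheduled surgery in the typical case, Section 9.2.3 follows only events already under way, and the 12-weekly visits have no AE assessment.

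Safety and tolerability of the combined regimen is a secondary endpoint (Section 2.2.2). A safety table built on these rules could show few wound complications because they were not asked for. How complete it was would vary between subjects with the date of surgery and with the passage that staff follow for the end of the window. Events not collected at the time may not be fully recoverable later.

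**Working it through.** **1. Inputs, with day 0 = last dose.** AE window ends on day 30 (Sections 6.4, 10.1, 12.1), or at a visit on day 23 to 37 (Table 2 and footnote p). Scheduled surgery is on day 28 or later (Section 6.2.1).

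**2. Post-operative days covered = max(0, window end − surgery day).** Scheduled surgery, no resumption:

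| Surgery day | Visit on day 23 | Day 30 | Visit on day 37 |
|---|---|---|---|
| 28 | 0 | 30 − 28 = 2 | 37 − 28 = 9 |
| 35 | 0 | 0 | 37 − 35 = 2 |
| 42 | 0 | 0 | 0 |

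If the last dose falls at the end of radiotherapy, days 28, 35 and 42 are surgery at 4, 5 and 6 weeks, the typical interval. From day 37 no last-dose reading gives any cover.

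**3. Decision-to-discontinue anchor.** With the decision D days after the last dose and surgery on day S, coverage = max(0, D + 30 − S). The documents give no value for D, so these are assumptions:

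| | D = 0 | D = 14 | D = 28 | D = 42 |
|---|---|---|---|---|
| S = 28 | 2 | 16 | 30 | 44 |
| S = 42 | 0 | 2 | 16 | 30 |

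**4. DLT period.** It ends 28 days after completion of concurrent treatment (Sections 3.1, 10.2.1). With surgery 4 to 6 weeks after radiotherapy, it closes at or before the operation.

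**5. Could the 12-weekly visits carry the collection alone?** With C1D1 as day 1, nominal visits fall on study days 85, 169, 253 and 337. Surgery on a visit day waits 169 − 85 = 84 days for the next. With the 2-week tolerance, a visit on day 71 (85 − 14) followed by one on day 183 (169 + 14) leaves 112 days. Surgery on day 71 is attainable: radiotherapy from day 8, 5 weeks of treatment and a 4-week interval give 8 + 35 + 28 = 71, assuming the last dose is no later than the end of radiotherapy. Visits also stop at recurrence, so record review is needed.

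**6. Precision of a descriptive wound rate** (exact 95% CI; the number resected is an assumption). With 40 resected: 0 events, 0 to 8.8%; 4 events, 2.8 to 23.7%; 10 events, 12.7 to 41.2%. With 30 resected: 0 events, 0 to 11.6%; 3 events, 2.1 to 26.5%; 10 events, 17.3 to 52.8%.

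**The case against.** **Serious events are already covered.** This largely stands. A reader might infer that major wound breakdown would go unreported, and the documents do not support that: related SAEs have no end date, possible relationship counts as related, and prolonged hospitalization from a surgical complication calls for an SAE report. What remains on the serious side is a smaller set, judged unrelated and not caught by Section 9.1.2.

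**The window follows drug exposure.** With the 99-hour half-life in Section 1.4, 28 days is 672 / 99 = 6.8 half-lives, leaving about 0.9% of the drug under simple exponential decay. That explains a 30-day limit for drug effects in general. It does not answer Table 8's own warning about late dehiscence, and the endpoint concerns a regimen that includes radiotherapy.

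**Coverage may be longer.** True if the decision to discontinue comes after the last dose, if the drug is resumed, or if surgery is unscheduled. None of these gives systematic collection for every resected subject.

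**The exam would reveal wound problems.** Clinically it may, and the findings survive in source documents. A reader might take Section 17.3 to bar entry of such an event, but the same rule on exam data applies inside the window, where AEs are logged separately. The obstacle is the closed window and the absence of an AE assessment in follow-up.

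**The recommended dose would be chosen without wound data.** A reader might infer this too, but the effect is limited. Section 3.1 does not make the choice wait for surgery, so the latest cohort's wound outcomes may not exist by then under any collection rule.

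**Collection is not free, and the rate would be uncontrolled.** Both stand. Chart review carries most of the work, and a single-arm rate cannot separate drug, radiotherapy and surgery.

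**Conclusion.** The point holds as a low-cost improvement in safety data collection. On the last-dose count, with scheduled surgery and no resumption, the earliest permitted operation has 2 post-operative days of routine recording (0 to 9 if tied to the 30-day visit), and surgery from day 37 has none. The decision-based count gives more only if the decision is later than the last dose, by a delay the documents do not state.

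The loss is mainly non-serious post-operative wound complications, which would not be systematically recorded on the eCRF. How many is unknown. Section 1.1.5 cites wound complications in 11 of 75 subjects in a pre-operative chemoradiation study, but it gives no split by seriousness, so the figure cannot be turned into a count of missed events.

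The consequence is an incomplete secondary safety endpoint. The primary endpoint, alpha, power and sample size are untouched. Nothing here shows the DLT definition to be wrong.

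**What to change.** 1. For resected subjects, record wound-related AEs under a stated definition, regardless of seriousness or attribution, over a fixed post-operative period chosen by the sponsor. Amend Table 2 and Sections 6.4, 9.1.1, 9.1.4, 10.1 and 12.1 to match.
2. Provide one eCRF page, completed at the existing 12-weekly visits and mainly by review of surgical records, including for subjects whose visits ended at recurrence.
3. Report the rate among resected subjects with an exact CI, labelled descriptive and as not separating drug, radiotherapy and surgery.
4. Use one AE-window anchor across Table 2 and Sections 6.4, 9.1.1, 9.1.4, 9.2.3, 10.1 and 12.1, and state how Sections 9.1.2 and 9.1.4 fit together for SAEs after the window.
5. Reconcile Section 9.2.3 with Section 12.1 on SAE follow-up, and Section 11 with Sections 11.1 and 6.4.1 on the end of concomitant-medication recording.
6. Have the sponsor reconcile Table 8 and Section 7.1.2 with Table 2 footnote i and Section 6.2.1 on resumption after surgery, because resumption moves the window. Which clinical rule applies is for the sponsor.
7. Leave the DLT definition unchanged.

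**Cost.** No new visit or procedure. It adds an eCRF page, chart-review time and data entry, and the safety table is likely to look less favourable.

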6.4.2. Long Term Follow-Up

Disease status and any subsequent anticancer therapy information status will continue to be monitored. All subjects that discontinue study drug and have not withdrawn full consent to participate in the study will continue in the follow-up phase. Follow up will continue to monitor disease status approximately every 12 weeks (± 2 weeks), until either one (1) year has elapsed since initiating cabozantinib therapy based on the date of C1D1, death, withdrawal of consent, disease recurrence, or the study closes, whichever is the earliest. This will include a physical exam and imaging assessment.

Thereafter, subjects will be followed for survival every 6 months (+/- 1 month) until 3 years have elapsed since initiating cabozantinib therapy based on the date of C1D1, disease recurrence, end-of-study, death, or withdrawal of consent, whichever is earliest. This evaluation may be made by review of publicly available information, record review and/or telephone contact.

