Follow-up Period	Follow-up period is the on-study time period after the EOT Visit. All subjects that discontinue study drug and have not withdrawn full consent to participate in the study will continue in the follow-up phase for disease recurrence. Follow up will continue approximately every 12 weeks (± 2 weeks), until either one (1) year has elapsed since initiation of cabozantinib therapy (C1D1), death, withdrawal of consent, disease recurrence, or the study closes, whichever is the earliest. This will include a physical exam and imaging assessment. Thereafter, subjects who will be followed every 6 months (+/- 1 month) until 3 years have elapsed since initiation of cabozantinib therapy (C1D1), end-of-study, death, or withdrawal of consent, whichever is earliest. This evaluation may be made by review of publicly available information, record review and/or telephone contact.
Primary Analysis	For this study will occur once all data for primary and secondary endpoints is collected.
Efficacy Analysis Dataset	This includes all subjects treated with at least one dose of cabozantinib at the recommended phase 2 dose, concurrently with neoadjuvant radiation therapy.
Full Analysis Set	All enrolled subjects who receive at least 1 dose of cabozantinib (treated population). Subjects enrolled to Phase 1 who withdraw for reasons other than toxicity during the DLT Period will be considered not evaluable and will be replaced.

Per-protocol Analysis Set	All enrolled subjects who do not have any prospectively defined protocol violations. Subjects enrolled to Phase 1 or Phase 2 who are unable to tolerate cabozantinib monotherapy will not be considered evaluable for the Phase 1 or 2 component of the study and will be replaced. Subjects enrolled to Phase 1 who withdraw for reasons other than toxicity during the DLT Period will be considered not evaluable and will be replaced.
Progression-free survival	The time from the first dose date to the first observation of a disease progression or death due to any cause.
Overall survival	The time from the first dose date to the date of death due to any cause.

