1.1.2. Standard Treatment

The therapy of non-metastatic sarcomas is dominated by surgery. In certain cases, definitive radiation therapy may be used, such as in subjects who are not candidates for surgery, or for whom the cosmetic or functional results of surgery are unacceptable. Surgery may be supplemented by adjuvant or neoadjuvant radiation therapy⁵. For certain subtypes of sarcomas (osteosarcoma, Ewing's sarcoma, rhabdomyosarcoma), the use of chemotherapy, administered prior to or after definitive local therapy with surgery or radiation, has demonstrated survival benefits. For most other types of sarcomas, the benefits of chemotherapy are unclear⁵.

For unresectable or metastatic STS, treatment is palliative⁵. Systemic chemotherapy remains the backbone of treatment. Surgery and/or radiotherapy may be useful to relieve symptoms, or, in a limited number of cases with uni- or oligo-metastatic disease, to provide definitive control. In subjects with unresectable disease, the life expectancy is limited, with median survival of approximately 12-18 months^{6,7}.

In treatment of primary disease, the surgical status of the tumoral margins (the presence of viable tumor at the edge of the resection specimen and the distance from the resection margin to the tumor) is an important indicator of outcome. Several systems exist for classifying the marginal status of tumors. One of the more widely used classifies tumor resection status into R0 (complete resection of grossly/macroskopically evident tumor, with no evidence of residual microscopic disease at the margins of resection); R1 (complete resection of grossly/macroskopically evident tumor, but with microscopically evident disease at the margins of resection); and R2 (gross/macroskopically evident disease remains after attempted resection).

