The second study randomized subjects undergoing a limb-sparing procedure to receive adjuvant radiation therapy (n=70) or no additional local therapy (n=71) [19]. For those with high histological grade, chemotherapy was administered concurrently with radiation. Local recurrence rates were suppressed, irrespective of histologic grade, with overall local recurrence of 1% in those treated with post-operative radiotherapy versus 24% in those not receiving radiotherapy. In the subset with high-grade tumors, no difference in metastatic disease-free or overall survival was evident based on radiotherapy assignment status.

These studies have some limitations^{19,20}. Both studies had relatively small sample sizes, especially the earlier study enrolling only 43 subjects, and both included chemotherapy in addition to post-operative radiotherapy. Local control was superior in both studies when radiation was included. No survival difference was observed based on administration of radiotherapy, implying that local control did not necessarily determine survival. The possibility of synergism between chemotherapy and radiation therapy was not addressed, nor were issues of toxicity. Neoadjuvant radiotherapy has not been compared to surgery alone.

The combination of surgery with either post-operative or pre-operative radiation therapy, the latter being the subject of this proposal, is quite effective in achieving local control of disease. One randomized study compared pre- and post-operative radiotherapy in treatment of extremity soft tissue sarcomas, with the primary endpoint of toxicity²¹. Among the 186 subjects evaluable for secondary efficacy measures, there was no difference in rate of local control, development of regional/distant relapse, and progression-free survival (log rank p=0.70, 0.79 and 0.83, respectively). Survival for post-operatively treated subjects was inferior (median follow-up=3.3 year; 85% alive pre-operative vs. 72% post-operative, log rank p=0.0481). This was due to an increased number of deaths due to sarcomas and to non-malignant causes in the post-operative group.

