2.2.2. Secondary endpoints

- Rate of pathologic response.
- Rate of surgical excision with negative margins.
- Response rate (complete, partial, overall) of the combination therapy prior to surgery, as defined by RECIST 1.1 criteria.
- Pattern of and time to local vs. distant recurrences.

- Relapse-free and overall survival at various time points from study entry.
- Safety and tolerability of combined treatment regimen.
- Rate of treatment discontinuation prior to neoadjuvant radiation therapy.

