^h Baseline scans should be done within 28 days prior to enrollment, preferably as close to C1D1 as possible. Repeat imaging should be completed every 12 weeks from C1D1 (+/- 2 weeks) for one year after initiation of protocol therapy based on the date of the C1D1 visit, or until disease recurrence/progression, withdrawal of consent, death, or end of study (whichever comes first) regardless of missed or out of window doses. MRI may be used if CT is contra indicated for a subject. The same mode of imaging at screening must be used consistently throughout the study. Baseline imaging must include CAP and the affected extremity. If subjects do not have disease in the A/P, imaging moving forward after baseline may omit those areas.

ⁱ Cabozantinib will be administered daily. Subjects will complete a daily drug diary during treatment, to be reviewed on Day 1 of each cycle. Subjects with at least stable disease at the first post-RT imaging timepoint may continue to receive cabozantinib therapy for a maximum of 6 cycles, with treatment ending at least 28 days prior to any scheduled surgery, including dental surgery.

^j Prior and concomitant medications, as well as any recent procedures should be documented at baseline. Prior medications/procedures include any medications or procedures completed ≤ 28 days prior to informed consent.

^k Follow up will continue to monitor disease status by imaging assessment of, at minimum, CT Chest and the affected extremity approximately every 12 weeks (± 2 weeks), until either one (1) year has elapsed since initiating cabozantinib therapy based on the date of the C1D1 visit, death, withdrawal of consent, disease recurrence, or the study closes, whichever is the earliest. Thereafter, subjects will be followed for survival every 6 months (+/- 1 month) until 3 years have elapsed since initiating cabozantinib therapy based on the date of the C1D1 visit, disease recurrence, end-of-study, death, or withdrawal of consent, whichever is earliest. This evaluation may be made by review of publicly available information, record review and/or telephone contact.

^m Lipid panel should be fasting.

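### Section 6.4.2 and Table 2 end survival follow-up at disease recurrence and the Definitions table does not; followed as written, the first two bias secondary overall survival upward

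*Combined protocol and SAP*

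**What the plan says.** Three places in the protocol describe the 6-monthly follow-up that runs to 3 years from C1D1.

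- Section 6.4.2, Long Term Follow-Up: "Thereafter, subjects will be followed for survival every 6 months", and this lasts "until 3 years have elapsed since initiating cabozantinib therapy based on the date of C1D1, disease recurrence, end-of-study, death, or withdrawal of consent". The first of these to occur ends it.
- Table 2, footnote k (Section 5): "until 3 years have elapsed since initiating cabozantinib therapy based on the date of the C1D1 visit, disease recurrence, end-of-study, death". Consent withdrawal completes the list, and recurrence is again a stop.
- Definitions table, Follow-up Period: "until 3 years have elapsed since initiation of cabozantinib therapy (C1D1), end-of-study, death, or withdrawal of consent, whichever is earliest". Recurrence is not listed.

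All three agree that recurrence ends the earlier phase of 12-weekly visits with imaging in year 1. They differ only on the later phase.

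The endpoint that this later phase serves is listed in Section 2.2.2 as "Relapse-free and overall survival at various time points from study entry". The Definitions table defines OS as "The time from the first dose date to the date of death due to any cause". Neither the definitions nor Section 12 states how OS is censored.

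**The concern.** Recurrence is a sensible end for a phase whose purpose is to detect recurrence. It is not a sensible end for a phase whose purpose is to record deaths, because most sarcoma deaths follow recurrence. A subject who leaves follow-up at recurrence is censored just as the hazard of death rises. Kaplan-Meier estimation assumes that censored subjects carry the same later risk as those who remain. Here they carry a higher one, so estimated OS is too high. Treating such subjects as alive in a simple proportion errs in the same direction.

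The wording is also unclear for recurrences in year 1. Recurrence closes the 12-weekly phase, and the word *Thereafter* may mean that the subject then moves into survival follow-up, or the recurrence stop may count as already met. Staff relying on different passages could collect some post-recurrence deaths and not others.

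What is at stake is the credibility of a secondary endpoint. OS carries no hypothesis or decision rule in this trial.

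**Working it through.** **Plan's own figure.** The documents give no numerical target for OS. The figure that can be checked is the primary sample size: null 75%, alternative 90%, one-sided alpha 0.10, power 90%. The normal approximation gives 39.2, so 40. The exact rule of at least 34 successes in 40 has alpha 0.096 and power 0.900. The 40 evaluable subjects in Section 12.4 are reproduced, and this point does not disturb them, because recurrence is itself a failure on the primary endpoint.

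**Inputs for the illustration.**
- 1-year relapse-free survival (RFS) of 0.75 or 0.90: Section 12.4.
- Median survival after recurrence of 12 or 18 months. Section 1.1.2 says of unresectable disease that "the life expectancy is limited, with median survival of approximately 12-18 months". Using it for survival after recurrence is an assumption; 36 months is added as a more favourable case.
- Constant hazards, and at first no deaths before recurrence: assumptions.

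**Model.** Recurrence hazard per year L = -ln(RFS at 1 year), which is 0.2877 or 0.1054. Hazard of death after recurrence m = ln 2 / median in years, which is 0.6931, 0.4621 or 0.2310. Then

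OS(t) = exp(-Lt) + [L/(m - L)] x [exp(-Lt) - exp(-mt)].

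Example, RFS 0.75 and median 12 months, t = 3: 0.4219 + (0.2877/0.4055) x (0.4219 - 0.1250) = 0.633.

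**Two readings.**
- *Strict*: any recurrence ends follow-up. No death is ever observed in this model, so the Kaplan-Meier estimate is 1.00 and the bias is 1 - OS(3).
- *Thereafter*: first-year recurrences are followed for survival, and later ones are censored at recurrence. After year 1 the estimated hazard at t is m x P(t) / [P(t) + exp(-Lt)], where P(t) is the proportion who recurred in year 1 and are alive at t. The estimate is OS(1) x exp(-integral of that hazard from 1 to 3).

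| 1-year RFS | Median after recurrence | True 3-year OS | Bias, strict | Estimate, *Thereafter* | Bias, *Thereafter* |
|---|---|---|---|---|---|
| 0.75 | 12 mo | 0.633 | 0.367 | 0.765 | 0.133 |
| 0.75 | 18 mo | 0.705 | 0.295 | 0.801 | 0.096 |
| 0.75 | 36 mo | 0.819 | 0.181 | 0.871 | 0.052 |
| 0.90 | 12 mo | 0.837 | 0.163 | 0.914 | 0.076 |
| 0.90 | 18 mo | 0.870 | 0.130 | 0.927 | 0.057 |
| 0.90 | 36 mo | 0.921 | 0.079 | 0.953 | 0.032 |

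**At 1 year.** True OS with the 12-18 month median is 0.927-0.948 (RFS 0.75) or 0.972-0.980 (RFS 0.90). The strict bias is therefore about 2-7 points. It is zero if first-year recurrences are followed.

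**Some deaths without recurrence.** If 10% of RFS failures are such deaths, the strict 3-year estimate is exp(-0.1 x L x 3) = 0.917 or 0.969. The bias is 0.306/0.240/0.138 (RFS 0.75) or 0.142/0.113/0.067 (RFS 0.90) for medians of 12/18/36 months.

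**Deaths not collected by 3 years, per 40 subjects.** The strict count is 40 x (1 - OS(3)): 14.7/11.8/7.3 (RFS 0.75) and 6.5/5.2/3.2 (RFS 0.90). Those arising from recurrences after year 1, which are the ones lost on the *Thereafter* reading, number 6.5/4.9/2.8 and 3.2/2.4/1.4.

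**The case against.** The strict reading fits poorly with the surrounding text. Section 6.4 is titled as follow-up for survival and start of anticancer therapy. Section 6.4.2 opens by saying that later anticancer therapy will be monitored and that all consenting subjects off drug stay in follow-up. Later therapy is mostly given after recurrence, so this points to continued contact. It makes the *Thereafter* reading more plausible for first-year recurrences, but it does not cancel the stop condition that follows, and on either reading deaths after later recurrences are lost.

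The larger figures also depend on the model. They censor at the instant of recurrence, whereas after year 1 recurrence may be learned only at a 6-monthly contact that could also reveal a death. Allowing for that, the ranges for the 12-18 month median fall to about 11-29 points (strict) and 4-8 points (*Thereafter*). The 12-18 month median belongs to unresectable disease, and some recurrences can be resected. With 36 months of enrolment in a 60-month study (Section 3.3), late enrollees may have only about 24 months of follow-up, which lowers the maximum count of missed deaths to about 14, or about 12 with contact-based ascertainment. These objections stand against the size, not the direction.

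Section 6.1 names a single centre, so differing practice between sites is a weak argument. Inconsistency within one centre remains possible.

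Section 15.4 lets the investigator search public records for survival status. That search is optional and is written for subjects who withdraw before completing their visits. It does not require anyone to ascertain deaths after recurrence.

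**Conclusion.** The concern holds. The three passages conflict, nothing says which governs, and no OS censoring rule fills the gap. If Section 6.4.2 and Table 2 are followed, secondary OS is biased upward. If the Definitions table governs, follow-up continues after recurrence and the problem does not arise.

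The direction is firm, resting only on recurrence raising the risk of death. The size is illustrative. With the 12-18 month median, 3-year OS is overstated by about 13-37 points on the strict reading and 6-13 on the other; with a 36-month median, by about 8-18 and 3-5. About 5-15 or 2-7 deaths per 40 subjects go uncollected with the shorter medians and full 3-year follow-up. The upper end needs 1-year RFS at the null value, a constant hazard to 3 years and the shortest median. Section 1.1.3 reports "85% alive pre-operative vs. 72% post-operative" at a median follow-up of 3.3 years. If true OS here is near that 85%, the bias cannot exceed 100 - 85 = 15 points.

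This should be fixed. It does not threaten the primary analysis, the sample size or the nine-failure stopping rule.

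**What to change.** 1. In Section 6.4.2 and Table 2, footnote k, delete disease recurrence from the conditions that end the 6-monthly survival follow-up, so that both match the Definitions table. Keep it as a stop for the 12-weekly phase.
2. State that recurrence at any time, including year 1, ends protocol imaging only, and that vital status is then collected every 6 months to 3 years from C1D1.
3. Add to Section 12 that subjects not known to have died are censored for OS at the date last known alive, not at recurrence.

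The cost is two deletions, two short statements, and a few extra record or telephone checks for each subject who recurs, by means Section 6.4.2 already permits. Vital status that is not collected prospectively may be hard to recover later.
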